4.3.1. Screen Failures

Screening includes informed consent, satisfaction of inclusion criteria and an initial survey of exclusion criteria. Rabies exposed subjects that are known to fail inclusion criteria at initial

screening or any immediately evaluable exclusion criteria will not be randomized into the study. They will be treated outside of the study protocol with the national standard of care for PEP. The minimum PEP standard will include equine rabies immune globulin (ERIG) or HRIG and rabies vaccination according to the national recommendations. Not all exclusion criteria need to be known at the time of randomization but those that are known will determine enrollment.

4.3.2. All Enrolled

The All Enrolled set includes every subject with recorded data in the Data Management (DM) database excluding screen failures.

4.3.3. As-Treated Population (Safety Population)

Since post-exposure treatment of rabies is urgent and should not be delayed, randomization and prophylaxis will begin after a screening event that includes informed consent and survey of inclusion criteria before some exclusion criteria have been confirmed. High-risk bite victims that meet all initially knowable inclusion/exclusion criteria will be randomized to receive study drug and begin a regimen of rabies vaccination. All subjects who are randomized and receive study drug are included in the “As-treated” Population. Unless otherwise specified, summaries of adverse events, treatment compliance, laboratory results, and vital signs will be based on the As-treated Population grouped by actual treatment received and overall.

4.3.4. LRG Per-Protocol Population

All subjects who

- are randomized
- receive the correct study drug
- have inclusion/exclusion criteria confirmed
- complete all rabies vaccinations scheduled
- lack major protocol deviations
- have adequate wound treatment and study drug injection of all exposure sites

will be included in the “Per-protocol” Population. Exclusion criteria that must be confirmed are the species of the biting animal; a high-risk exposure (WHO Category 3); interval ≤ 54 hours from the bite to the start of prophylaxis; the absence of RVNA ≥ 0.1 IU in serum obtained at Study Day 1, time “0” blood collection (WHO, 2013). Subjects who are discovered to not have satisfied criteria for the Per-protocol Population may be excluded from that population by the Per-protocol Adjudication Board.

4.3.5. NRG Per-Protocol Population

All subjects who

- are randomized
- receive the correct study drug
- have inclusion/exclusion criteria confirmed

- complete all rabies vaccinations scheduled
- lack major protocol deviations
- have adequate wound treatment and study drug injection of all exposure sites
- are not part of the LRG enrollment

will be included in the “Per-protocol” Population. Initial exclusion criteria that must be confirmed are the species of the biting animal; a high-risk exposure (WHO Category 3); interval ≤ 54 hours from the bite to the start of prophylaxis; the absence of RVNA ≥ 0.1 IU in serum obtained at Study Day 1, time “0” blood collection (WHO, 2013). Subjects who are discovered to not have satisfied criteria for the Per-protocol Population may be excluded from that population by the Per-protocol Adjudication Board.

5. Subject Disposition

5.1. Disposition

The subject disposition table summarizes the counts for each analysis set and summarizes the reason for discontinuation from study by total and frequency.

5.2. Protocol Deviations

All protocol deviations (including violations) will be assessed and reviewed at the BDRM prior to the database lock. Any exclusion of randomized subjects from the Per-protocol Population after randomization must be made by the Per-protocol Adjudication Board. Subjects with the following significant deviations will be excluded from the Per-protocol Populations:

- Defective informed consent
- Received the incorrect study drug
- Received the incorrect dose ($\pm 20\%$) of study drug
- Failed to complete the scheduled rabies vaccinations through Study Day 29
- Are discovered to lack adequate prophylactic treatment of all exposure sites
- Are discovered to be injured by animal other than those listed
- Are discovered to have an interval >54 hours from rabies exposure to the start of prophylaxis
- Are discovered to have RVNA ≥ 0.1 IU in serum obtained at Study Day 1
- Receive prohibited treatment during the trial
- Are found not to have a modified WHO Category 3 exposure
- Are discovered to have or have developed HIV infection or other immunodeficiency state
- Second high-risk animal bite or contact requiring PEP

As the study is ongoing, additional significant protocol deviations can also be identified or defined by the Per-protocol Adjudication Board. The list of significant protocol deviations can be updated accordingly.

Significant deviations categorized according to the list will be summarized in a table for the As-treated Population. All protocol deviations will be presented in a listing and an additional listing

of deviations for the randomized subjects who missed any dose of study drug or rabies vaccine will be provided.

6. Demographics and Baseline Characteristics

Demographic parameters (age, gender, race and ethnicity), randomization factors (including study site and bite location) and other baseline characteristics will be summarized by treatment group for all subjects in the As-treated Population. The summary can be used to check potential imbalance between treatment groups.

6.1. Demographics

Demographics for all subjects in the As-treated Population will be presented in a listing. Listings of randomized subjects who missed any dose of study drug or rabies vaccine and of subjects with protocol deviations will be provided.

The age and body mass index (BMI) collected in CRF will be used for analysis if it is non-missing. If the age is not collected in the CRF, the age in years is calculated using the date of the informed consent and date of birth.

Age (years) = [(Informed Consent Date – Date of Birth + 1) / 365.25].

6.2. Baseline Disease Characteristics

All rabies related characteristics as captured on the ‘Confirmation Visit’ and ‘Bite Wound Washing or Irrigation’ CRF pages will be summarized as recorded based on the As-treated Population.

6.3. Medical History

Medical history will include, but is not limited to, events recorded on the Medical History CRF page. Any event that is proven to have ended before the first dose of study drug will also be categorized as a medical history. Medical history will be coded using the Medical Dictionary for Regulatory Activities (MedDRA), version 21.0 or later (the actual MedDRA version used will be specified in the actual outputs). The number and percentage of subjects with any medical history will be summarized by treatment group and overall for each system organ class (SOC) and preferred term (PT). Percentages will be calculated based on the number of subjects in the As-treated Population.

6.4. Inclusion and Exclusion Criteria

Prior to enrollment, the investigator will assess if the subject fulfills all the inclusion and none of the exclusion criteria outlined in the protocol. The specific inclusion criterion not met or exclusion criterion which was met will be recorded in the CRF. This information and whether the sponsor granted a waiver will be presented in a listing.

6.5. Electrocardiogram

Baseline ECG results and overall interpretation will be listed and summarized by risk group and treatment based on the As-treated Population. If abnormal, clinically significant findings should be considered a pre-existing condition and be indicated on the Medical History CRF page.

7. Treatments and Medications

7.1. Prior and Concomitant Medications

The collection of information on concomitant medications used by subjects following study drug administration will coincide with the collection period of adverse events. The collection period for concomitant medications associated with the treatment of adverse events will be 42 days following the last study drug. The collection period for concomitant medications associated with the treatment of serious adverse events (SAE) will be Study Days 1-365. The collection period for prohibited medications will be Study Days 1-365.

Concomitant medication includes prescription and non-prescription drugs or other treatments, and any vaccines other than rabies or tetanus vaccines specified by the protocol. The name of the medication, treatment start and stop dates (or ‘ongoing’), route of administration, and indication must be recorded on the ‘Concomitant Medications’ CRF. The indication recorded on the ‘Concomitant Medications’ CRF must correspond to a medical term/diagnosis recorded on the AE CRF, or to a pre-existing condition noted in the subject’s medical history, or be noted as prophylaxis, e.g., dietary supplement.

Prohibited medications include any vaccination or immunoglobulin directed against rabies. Systemic corticosteroids or other immunosuppressants administered within 29 days of first rabies vaccination are prohibited.

All prior and concomitant medications will be coded using the World Health Organization Drug Dictionary Enhanced (WHO-DD) and summarized by treatment group based on the As-treated Population. The actual dictionary version used will be specified in the actual outputs.

7.1.1. Prior Medications

Prior medications are defined as medications taken and stopped prior to the first dose of study drug. Prior medications will only be presented in a data listing.

7.1.2. Concomitant Medications

Concomitant (including post-treatment) medications are defined as medications with a start date or a stop date occurring on or after the first dose. If the medication start/stop date is missing or partial, the medication will be considered concomitant unless there is evidence to the contrary (e.g., month and year of stop date is present and is less than the month and year of the first dose of study drug). (Section 15.3.2)

A frequency summary table based on the drug class (Anatomical Therapeutic Chemical (ATC) level 2 terms) and standardized medication names will be produced. At each level of

summarization, a subject is counted once if he/she received one or more medications at that level.

A by-subject listing of concomitant medications will be provided.

7.2. Treatment Exposure and Compliance

7.2.1. Extent of Exposure

Extent of exposure including number of doses, cumulative number of doses, duration of exposure, and cumulative dose will be summarized for the As-treated Population as well as the Per-protocol Population. Percentages will be calculated based on number of subjects in the specified population.

Duration of treatment exposure (days) will be calculated as (date study drug last applied minus date study drug first applied) plus 1.

7.2.2. Treatment Compliance and Modifications

Compliance will be summarized for rabies vaccinations. Treatment compliance is defined as the ratio of total number of vaccinations to the planned number of vaccinations, in terms of percentage. Treatment compliance will be summarized descriptively for both the As-treated and the Per-protocol Populations.

8. Efficacy Analysis

The primary and secondary efficacy endpoints may be performed on the As-treated and the Per-protocol Populations. The Per-protocol analyses will be considered primary; the As-treated analyses will be considered supportive. The denominator for all percentages will be the number of subjects in that treatment within the analysis set of interest, unless otherwise specified.

8.1. Primary Efficacy Endpoint

The primary objective will be evaluated by a composite endpoint with four elements in three areas:

- the geometric mean RVNA concentration for SYN023 recipients is superior to the geometric mean RVNA concentration for HRIG recipients on Study Day 8
- the immune response to rabies vaccine on Study Day 99: RVNA geometric mean titer (GMT) noninferiority SYN023 vs HRIG
- the response to rabies vaccine on Study Day 99: RVNA ≥ 0.5 IU/mL % noninferiority SYN023 vs HRIG
- the absence of clinical rabies.

The primary efficacy analyses will be performed on the Per-protocol Population for the NRG group. Standard log transformation on GMC can be found in Section 15.2.

8.1.1. Primary Analysis

8.1.1.1. Superiority Testing on Study Day 8

The first element is superiority of the geometric mean concentration of RVNA (serum) in SYN023 recipients on Study Day 8. RVNA was selected because it is a generally accepted surrogate for rabies vaccine protection. If it is possible to demonstrate quicker and higher concentrations in the blood of RVNA from SYN023 then this may be evidence of greater potency and perhaps effectiveness.

GMC for a group of subjects is calculated by multiplying all values and taking the n th root of this number, where n is the number of subjects with available data. Because concentrations are often approximately log-normally distributed, they are customarily analyzed on a logarithmic (log) scale; a difference in arithmetic means (Δ) on a log scale becomes a ratio of geometric means (\emptyset) when the results of analysis are converted back to the original data scale. Thus, each hypothesis is a statement regarding \emptyset . The alternative hypothesis (H_a) is that the SYN023 vaccine is superior to HRIG.

$$H_a: \emptyset = \frac{GMC_{SYN023}}{GMC_{HRIG}} > 1$$

The null hypothesis is the complement of the alternative, meaning that the SYN023 vaccine is inferior or equal to HRIG.

$$H_0: \emptyset = \frac{GMC_{SYN023}}{GMC_{HRIG}} \leq 1$$

The null hypothesis will be rejected at a significance level of 2.5% ($\alpha = 0.025$) if the lower bound of the one-sided 97.5% confidence interval (CI) for the GMC ratio is greater than 1.

In the summary table, by-treatment GMCs and geometric standard deviations (Geo SDs) will be displayed, where Geo SD is calculated by converting the normal concentration values in to log-normal values, calculating the typical standard deviation of log transformed concentrations and then taking its antilog for the geometric standard deviation. GM ratio along with its coefficient of variation (CV) and 95% CI will also be displayed in the summary table.

8.1.1.2. Non-inferiority Testing on Study Day 99

The second element is immune response to the rabies vaccine on Study Day 99 measured by the noninferiority of the Study Day 99 GMC of RVNA in SYN023 recipients compared to Study Day 99 GMC of RVNA in the HRIG recipients. Synermore defines non-inferiority rabies vaccine response as a 20% margin of non-inferiority and equal allowance (number of subjects in SYN023 = number of subjects in HRIG) and alpha is taken to be 0.025.

The alternative hypothesis (H_a) is that the SYN023 vaccine is non-inferior to HRIG by a 20% margin.

$$H_a: \emptyset = \frac{GMC_{SYN023}}{GMC_{HRIG}} > 0.8$$

The null hypothesis is:

$$H_0: \emptyset = \frac{GMC_{SYN023}}{GMC_{HRIG}} \leq 0.8$$

The null hypothesis will be rejected at a significance level of 2.5% ($\alpha = 0.025$) if the lower bound of the one-sided 97.5% confidence interval for the GMC ratio is greater than the non-inferiority bound 0.8. Descriptive statistics will be displayed in a summary table following the same presentation for Section 8.1.1.1.

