Day 112	73	1.43	(1.09, 1.87)	76	1.71	(1.38, 2.11)

Non-Inferiority test for ratio of two geometric means is used for determining the sample size. The null hypothesis is that the ratio for the two treatments is less than the defined margin which is expressed as:

$$H_0: \emptyset \leq \emptyset_L \text{ where } \emptyset_L < 1$$

The alternative hypothesis for superiority is $H_1: \emptyset > \emptyset_L$. The calculated ratio between SYN023/RIG and the 95% confidence intervals for the ratio are presented in Table 7.8.2-2 and were used as inputs for the sample size calculation in PASS 15 software.

Table 7.8.2-2: Ratio (SYN023/HRIG) and 95% Geometric Confidence Intervals for Each Time-point for RVNA from SYN023-002 Protocol, Historical Data

Time Point	Ratio (SYN023/HRIG) for RVNA- SYN023-002	95% Geometric Means Ratio CI		CV
Day 35	81.28%	62.19%	106.23%	13.59%
Day 42	88.94%	68.79%	114.99%	13.04%
Day 84	88.50%	64.04%	122.30%	16.47%
Day 112	86.94%	61.88%	122.15%	17.32%

The sample size is calculated at 80% power with 20% margin of non-inferiority and equal allowance (number of subjects in group 1 = number of subjects in group 2) and alpha is taken to be 0.025.

The non-inferiority of serum GMC RVNA on study day 84 in SYN023 recipients (above) with respect to HRIG recipients would require the sample size of 138 for 80% power with an expected true geometric means ratio 88.00%. Note that based on historic data from protocol SYN023-002 the geometric ratio from Study Day 42 through Study Day 112 is stable and therefore it is expected that a true ratio of 88.00% is reasonable to determine non-inferiority at Study Day 99.

7.8.3 Non-inferiority of Percentage of Subjects with Serum RVNA ≥ 0.5 IU/mL on Study Day 99

20 % margin of noninferiority was selected since it is a recommended bioequivalence margin for a lower bound of 0.8 (FDA 2001). Historical SYN023 data is presented In Table 7.8.3-1.

Table 7.8.3-1 Historical Percentage of Subjects with RVNA ≥ 0.5 IU/mL

DAY	SYN023 + Vaccine		RIG + Vaccine	
	≥ 0.5 IU/mL Count (percentage)	Total	≥ 0.5 IU/mL Count (percentage)	Total
0	3 (4.0%)	75	1 (1.3%)	76
1	67 (90.5%)	74	1 (1.3%)	75
3	74 (98.7%)	75	1 (1.3%)	76
7	75 (100.0%)	75	6 (7.9%)	76
14	75 (100.0%)	75	75 (98.7%)	76
28	75 (100.0%)	75	76 (100.0%)	76
35	74 (100.0%)	74	74 (100.0%)	74
42	73 (100.0%)	73	76 (100.0%)	76
84	72 (100.0%)	72	75 (100.0%)	75
112	70 (95.9%)	73	75 (98.7%)	76

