2.2. Secondary Objective(s)

- To demonstrate that the geometric mean RVNA concentration for SYN023 is superior to the geometric mean RVNA concentration for HRIG on Study Day 4.
- To demonstrate that the geometric mean RVNA AUEC₁₋₁₅ for SYN023 is superior to the geometric mean RVNA AUEC₁₋₁₅ for HRIG
- To describe the ratio of the geometric mean concentrations of RVNA at each time point in SYN023 recipients divided by the geometric mean concentrations of RVNA in HRIG recipients for LRG and NRG in the Per-protocol and As-treated Populations.
- To describe the percentage of RVNA concentration ≥ 0.5 IU/mL at each time point for SYN023 and HRIG recipients for LRG and NRG in the Per-protocol and As-treated Populations.
- To describe the pharmacokinetics of SYN023 using non-compartmental analysis. V_d , C_{max} , T_{max} , AUC_{1-t} , AUC_{1-inf} , $t_{1/2}$, Cl , and λ_z will be calculated when possible in the LRG and NRG Per-protocol and As-treated Populations.

- To evaluate presence and effects of anti-SYN023 antibodies (anti-CTB011, anti-CTB012).
- To evaluate the safety of SYN023 compared to HyperRab® S/D.
- To describe any effect of increasing BMI on SYN023 and RVNA concentrations.

3. Investigational Plan

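### The Day 99 GMC non-inferiority test is unadjusted although age, sex and, where recorded, BMI are available at baseline: a valid test, but possibly some avoidable loss of precision

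*SAP*

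**What the plan says.** SAP 8.1.1.1 defines the estimator: "GMC for a group of subjects is calculated by multiplying all values" and taking the nth root, with the comparison made on the log scale. SAP 8.1.1.2 applies it to Day 99 and declares non-inferiority if the "lower bound of the one-sided 97.5% confidence interval for the GMC ratio is greater than the non-inferiority bound 0.8". SAP 8.2 tests Day 4 and AUEC1-15 for superiority with the same presentation. No regression model and no covariate is named for any of these tests.

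Baseline data have two other uses. SAP Section 6 tabulates age, sex, race, ethnicity, site, bite location and other characteristics by arm, and says of the table: "The summary can be used to check potential imbalance between treatment groups". Protocol 7.2 likewise says that imbalance will be examined. Neither document says what follows if imbalance is found. BMI also appears in a descriptive secondary objective, "To describe any effect of increasing BMI on SYN023 and RVNA concentrations", which SAP 8.2 presents in SYN023 recipients only. SAP 6.1 uses the CRF age and BMI when they are not missing.

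**The concern.** The primary objective requires all its elements to succeed. Among the tested primary elements, Protocol Table 7.8-1 gives Day 99 GMC non-inferiority the largest sample size: 138, against fewer than 10 for Day 8 and 72 for the Day 99 percentage. Precision matters most there.

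If age, sex or BMI predict log RVNA, a pre-specified adjustment narrows the interval and removes chance imbalance in those variables. The hypothesis, margin and alpha stay as they are. Baseline RVNA, the usual first choice of covariate, has little to offer because the per-protocol set excludes Study Day 1 values of 0.1 IU or more. With nothing pre-specified, any adjustment made after looking at the imbalance table would be post hoc.

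**Working it through.** **The plan's own figure.** Protocol 7.8.2 states: "The sample size is calculated at 80% power with 20% margin of non-inferiority", with one-sided alpha 0.025, and that this "would require the sample size of 138 for 80% power with an expected true geometric means ratio 88.00"%. Table 7.8-1 gives a CV of 17.00%. With log SD = sqrt(ln(1 + 0.17²)) = 0.169 and distance ln(0.88/0.80) = 0.0953, a noncentral-t calculation gives a total of 102, not 138. The Day 112 row of Table 7.8.2-2 (ratio 0.8694, CV 17.32%) gives 138.

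**Between-subject SD.** From the GMC intervals in Protocol Table 7.8.2-1, SD = ln(U/L)/(2t) × √n:

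| | Interval | n | Log SD |
|---|---|---|---|
| Day 84 SYN023 | 1.79–3.03 | 72 | 1.12 |
| Day 84 HRIG | 2.27–3.33 | 75 | 0.83 |
| Day 112 SYN023 | 1.09–1.87 | 73 | 1.16 |
| Day 112 HRIG | 1.38–2.11 | 76 | 0.93 |

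Pooled, this is 0.98 at Day 84 and 1.05 at Day 112; I use 1.0. The CVs printed in Table 7.8.2-2 are a different quantity. The Day 84 ratio interval (64.04% to 122.30%) implies a standard error of ln(1.2230/0.6404)/(2 × 1.976) = 0.164 for the log ratio, which matches the printed 16.47%.

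**Effect of adjustment.** The plan requires 320 per-protocol subjects, 160 per arm. R² is the share of log-RVNA variance explained by age, sex and BMI. It is an assumption, because the documents give no figure.

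- Half-width of the log ratio = 1.96 × 1.0 × sqrt(2(1 − R²)/160).
- Equivalent unadjusted size per arm = 160/(1 − R²).
- Power from the noncentral t, one-sided 0.025, bound 0.8, with three degrees of freedom lost when adjusted.

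| R² | Half-width | Equivalent n per arm | Power, ratio 1.0 | Power, ratio 0.88 |
|---|---|---|---|---|
| 0 (unadjusted) | 0.219 | 160 | 51% | 13% |
| 2% | 0.217 | 163 | 52% | 14% |
| 5% | 0.214 | 168 | 53% | 14% |
| 10% | 0.208 | 178 | 55% | 14% |
| 15% | 0.202 | 188 | 58% | 15% |

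The observed ratio needed to pass falls from 0.8 × exp(0.219) = 0.996 to 0.8 × exp(0.202) = 0.979 at R² = 15%. An observed ratio of 0.88 fails either way: its lower bound is 0.88 × exp(−0.219) = 0.707 unadjusted and 0.88 × exp(−0.202) = 0.719 at R² = 15%.

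**Early time points.** Table 7.8-1 expects ratios above 10 with fewer than 10 subjects for Day 8 and for the other early row (labelled Study Day 3, which is Study Day 4 in the trial's day numbering). Adjustment has no practical effect there.

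**Missing BMI.** SAP Section 4 imputes nothing except partial dates, so a complete-case model would drop subjects without BMI. Losing 5% of subjects (152 per arm) cancels the gain at R² = 5%, since 2 × 0.95/152 = 2/160.

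**The case against.** The strongest reply is that nothing here is wrong. Arms are allocated 1:1, the decision rule is explicit, and an unadjusted comparison of log means is a valid test. That stands. Post-randomisation exclusions from the per-protocol set give adjustment some extra appeal, but they do not make the unadjusted test invalid.

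A reader might infer three stronger claims that the documents do not support:

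- **That the interval is certainly wider than necessary.** This holds only if the covariates predict log RVNA. At R² = 2% the narrowing is about 1%; at zero there is none.
- **That every subject has a BMI.** SAP 6.1 allows for missing values, and the visit schedules list no height or BMI measurement. Weight is needed for dosing; height is not shown.
- **That the plan regards BMI as a determinant of the Day 99 response.** The BMI objective is descriptive and displayed in SYN023 recipients only. The protocol holds that administered antibody will have dissipated by Day 99, so that values reflect vaccination.

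It can also be said that the head, neck or genitalia bite stratum and site have the better claim to a place in a model, since allocation takes them into account. They are also absent from the analysis, but that is a separate question, and leaving them out does not make adjustment for age, sex and BMI unsound.

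**Conclusion.** The point holds as a possible, modest loss of precision and a gap in pre-specification. For assumed R² of 2% to 15%, the Day 99 half-width shrinks by about 1% to 8%, worth 3 to 28 extra subjects per arm. This rests on log SD 1.0, 160 per arm, and covariates that do predict RVNA.

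It would be wrong to conclude that adjustment rescues the Day 99 element. At the planned ratio of 0.88, power stays near 13% to 15%. Reaching 80% with 320 subjects would need a residual SD of about 0.30, or R² of about 1 − 0.30² = 91%. The low power comes from the variability assumed in the sample-size calculation, which is a separate and larger problem.

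**What to change.** In SAP 8.1.1.2, and for consistency in 8.1.1.1 and 8.2 (Day 4 and AUEC1-15), pre-specify a linear model on the log-transformed outcome with treatment, age (continuous), sex and BMI (continuous). Back-transform the adjusted difference and its 95% CI to a GMC ratio, apply the existing decision rule, and report the unadjusted ratio as a sensitivity analysis. This would also supply a two-sample interval method, since SAP 15.2 describes only a one-group interval.

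Keep every subject in the model by replacing a missing BMI with the pooled mean, computed blind to treatment, and state this as an exception to the no-imputation rule in SAP Section 4. If BMI is not routinely recorded, drop it from the model.

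The cost is a few lines of SAP text before unblinding and three degrees of freedom out of more than 300 (320 − 2 − 3 = 315 remain). If the covariates prove weak, there is little or no gain.
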